6.2. Appendix 2 Data Derivations Rule

6.2.1. Number of Occurrences of Each AE

For solicited administration-site and systemic AEs, the number of occurrences will be:

Equal to zero if the leading question ‘Did the AE occur?’ is ‘No’ or ‘Not done/Unknown’.

Equal to one if the leading question ‘Did the AE occur?’ is ‘Yes’.

For unsolicited AE, AEs with different PTs and/or start dates will be counted as distinct occurrences in a same patient.

6.2.2. Duration of Each AE

The duration of each solicited AE during the solicited event period (Day 1 to Day 7), in days, will be summarized using descriptive statistics (n, mean, SD, minimum, median and maximum).

For solicited AEs, if the AE leading question ‘Did AE occur?’ is ‘Yes’, then the duration will be calculated as the sum of the individual days when the AE occurred: defined as ‘Day X occur?’ being ‘Yes’ or ‘Not done/Unknown’.

Example: AE leading question ‘Did AE occur?’ is ‘Yes’.

Day 1	Day 2	Day 3	Day 4	Day 5	Day 6	Day 7	AE Duration
Yes	Not Done/ Unknown	Not Done/ Unknown	Yes	No	No	No	4 days

Day 1	Day 2	Day 3	Day 4	Day 5	Day 6	Day 7	AE Duration
Yes	No	No	Yes	Yes	Yes	Yes	5 days
Not Done/ Unknown	7 days						

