6.4.4 Safety Analyses

All safety analyses will be performed on the Exposed Set and Solicited Safety Set.

For the analysis of vaccine safety, the following parameters and the 95% CI will be calculated:

- The percentage of participants with at least 1 local AE (solicited and/or unsolicited), with at least 1 general AE (solicited and/or unsolicited) and with any AE during the solicited follow-up period after vaccination will be tabulated with exact 95% CI.
- The percentage of participants reporting each individual solicited local (any, Grade 3) and general (any, Grade 3, related, Grade 3 related, medically attended) AE during the solicited follow-up period after vaccination will be tabulated with exact 95% CI.
- The duration statistics (in terms of number of days) of each solicited local and general AE during the 7 day post-vaccination follow-up period will be tabulated.
- The percentage of participants reporting ongoing solicited (local and general) AEs at the end of the solicited follow-up period will be tabulated with exact 95% CI.
- Temperature will be reported per 0.5°C cumulative increments beginning with temperature 37.5°C/99.5°F.
- The percentage of participants with at least 1 report of an unsolicited AE (any, Grade 3, related, Grade 3 related) classified by the MedDRA during the follow-up period will be tabulated with exact 95% CI.
- The proportion of participants who started to receive at least 1 concomitant medication during the follow-up period will be tabulated with exact 95% CI.
- The percentage of participants with at least 1 report of SAE classified by MedDRA during the trial period will be tabulated with exact 95% CI.
- The percentage of participants with at least 1 report of a medically attended event classified by MedDRA during the trial period will be tabulated with exact 95% CI.
- SAEs and withdrawals due to AE(s) will be described in detail in Listings.

CONFIDENTIAL

Phase IV Clinical Trial Protocol

GlaxoSmithKline
A phase IV trial of *Fluarix Tetra* in Indian
adults aged 65 years and older
Version 2.0, dated: 05 May 2023
Protocol/ Study No.: 218702
Page 57 of 74

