6.2.3. Handling of Missing Data

It is optimal to prevent missing data, to the extent possible, through strategies set forth in the design and conduct of a trial. For the current trial, we will aim to minimize missing information; for a given participants and a given immunogenicity measurement, missing or non-evaluable measurements will not be replaced.

The data will be analyzed as they are recorded in the trial eCRF. The number of missing values for data elements will be reported in tables and listings. Missing relationship with study vaccine, and outcome of unsolicited AEs will not be replaced and will appear as 'Missing' when displayed in a listing.

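### When a solicited AE is reported, SAP 6.2.2 counts every 'Not done/Unknown' diary day as an event day, so the only planned duration is an unlabelled upper bound

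*SAP*

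**What the plan says.** SAP 6.2.2 covers "The duration of each solicited AE during the solicited event period (Day 1 to Day 7), in days", summarised by n, mean, SD, minimum, median and maximum. A duration is derived only when the leading question for that AE is 'Yes'. In that case "then the duration will be calculated as the sum of the individual days when the AE occurred", with such a day "defined as ‘Day X occur?’ being ‘Yes’ or ‘Not done/Unknown". Three worked examples give 4, 5 and 7 days; the last has no 'Yes' day.

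Protocol 6.4.4 plans the result: "The duration statistics (in terms of number of days) of each solicited local and general AE during the 7 day post-vaccination follow-up period". Protocol 6.4.2 lists the same table among the primary endpoint analyses. SAP 4.4.1.7 places it with the other safety analyses, on the Solicited Safety Set, and points to 6.2.2. The protocol has no rule for unknown diary days.

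Two other SAP rules bear on this. For the number of occurrences of a solicited AE, SAP 6.2.1 has "Equal to zero if the leading question ‘Did the AE occur?’ is ‘No’ or ‘Not done/Unknown". SAP 6.2.3 states generally: "The data will be analyzed as they are recorded in the trial eCRF", and adds that numbers of missing values will be reported.

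**The concern.** An unknown day is not an observed event day, yet the rule adds the two together and the sum is the only duration planned. A reader of the table cannot tell a week of recorded pain from one recorded day followed by a blank card.

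Incomplete cards are foreseeable. Participants aged 65 and over fill in a paper card daily, it is collected at Day 22, and Protocol 6.4.6 itself expects that reporting will depend on willingness to complete it. Under the footnote to SAP section 3, a card counts as returned once solicited AE data are in the database, so partly completed cards enter the Solicited Safety Set.

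At stake is a descriptive reactogenicity result in a trial whose primary objective is reactogenicity and safety. With a single arm, no comparator shares the convention. One record with all seven days unknown is enough to set the maximum for that AE to 7 days.

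**Working it through.** **Inputs.** From SAP 6.2.2: the window is 7 days, a duration exists only if the leading question is 'Yes', and both 'Yes' and 'Not done/Unknown' days count. The rate of unknown days and the true durations are not in either document, so they are assumed below and varied.

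**Reproducing the SAP's examples.** Let Y be the number of 'Yes' days and U the number of unknown days. The SAP duration is Y + U.

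- Example 1 (Yes, unknown, unknown, Yes, No, No, No): 2 + 2 = 4. SAP: 4.
- Example 2 (Yes, No, No, Yes, Yes, Yes, Yes): 5 + 0 = 5. SAP: 5.
- Example 3 (no 'Yes' day): 0 + 7 = 7. SAP: 7. The row is collapsed in the text available here. It is read as seven unknown days, because under the rule no other pattern without a 'Yes' gives 7.

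**What the diary supports.** The longest compatible duration is Y + U. The shortest is max(1, Y), taking at least one event day because the leading question is 'Yes'.

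| Record (leading question 'Yes') | SAP | Compatible range | 'Yes' days plus unknown days between two 'Yes' days |
|---|---|---|---|
| Example 1 | 4 | 2 to 4 | 4 |
| Example 2 | 5 | 5 | 5 |
| Example 3 | 7 | 1 to 7 | unknown |
| 'Yes' on Day 1, then six unknown | 1 + 6 = 7 | 1 to 7 | 1 |
| Two unknown, five 'No' | 0 + 2 = 2 | 1 to 2 | unknown |

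The SAP value is the upper end in every row. Over the SAP's three examples the mean is (4 + 5 + 7)/3 = 5.33 days, against a lower bound of (2 + 5 + 1)/3 = 2.67 days.

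**Illustrative size.** Assume a true duration of d days and that each day is unknown with probability u, independently of whether the event was present. The d event days count either way, and each of the 7 − d event-free days is counted with probability u:

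expected SAP duration = d + u(7 − d)

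| u | d = 1 | d = 2 | d = 3 |
|---|---|---|---|
| 2% | 1.12 (+12%) | 2.10 (+5%) | 3.08 (+2.7%) |
| 5% | 1.30 (+30%) | 2.25 (+12.5%) | 3.20 (+6.7%) |
| 10% | 1.60 (+60%) | 2.50 (+25%) | 3.40 (+13.3%) |
| 20% | 2.20 (+120%) | 3.00 (+50%) | 3.80 (+26.7%) |

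For example, d = 2 and u = 10% gives 2 + 0.10 × 5 = 2.50. With u = 0 there is no inflation. If instead a share f of reporters have all seven days unknown and the rest have complete cards, the mean at d = 2 is (1 − f) × 2 + f × 7 = 2 + 5f, which gives the same figures.

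**Bias in the other direction.** Under the same model, counting 'Yes' days alone gives d(1 − u). At d = 2 this is 1.96, 1.90, 1.80 and 1.60 days for u = 2%, 5%, 10% and 20%, so it is low by 2% to 20%. Setting aside records with no 'Yes' day (probability u² at d = 2) narrows this slightly: at u = 20%, 1.60/(1 − 0.04) = 1.67. Neither count is unbiased, but under this model the two bracket the true value.

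**The case against.** The strongest defence is that this is a pre-specified worst-case convention, explained with examples, in a safety analysis where overstatement is the safer error. SAP 6.2.3.1 takes the same line by setting missing severity to the highest grade observed. Missing data may also come from sicker participants: the one cause of non-completion that Protocol 5.5.2 names is hospitalization. If recording stops during an ongoing event, dropping the later unknown days understates duration. Unknown days should also be limited by the Day 8 call with diary assessment, the completeness review at Day 22 (Protocol Table 2) and the eCRF edit checks (Protocol 7.6). The planned median is less sensitive to a few 7-day values than the mean.

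Much of this stands. It is a good reason to keep the worst-case count, but not to show it alone and unlabelled. Nor is the convention uniform: SAP 6.2.1 counts an unknown leading question as no occurrence. Reporting numbers of missing values, as SAP 6.2.3 plans, does not show which durations rest on them.

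Some stronger readings are tempting, but the documents do not support them:

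- *That every participant without a recorded event day gets 7 days.* This needs a leading question of 'Yes' and all seven days unknown. Two unknown and five 'No' days give 2. A leading question of 'No' or unknown gives no duration at all.
- *That 6.2.2 flatly contradicts 6.2.3.* The as-recorded statement is general, and its own subsections impute severity and dates. SAP 6.2.2 is a specific rule beside it.
- *That the durations will be inflated, chiefly by short, mild reactions in people who stop recording.* Neither document gives an unknown-day rate or links stopping to mild events.

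**Conclusion.** The concern holds within limits. For every AE reported as 'Yes', the planned duration is the upper end of what the diary allows, and nothing in the table will say so. The bias is upward whenever an unknown day was event-free, and zero if there are no unknown days.

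Its size cannot be derived from the documents. The range of 5% to 50% at a true duration of 2 days rests on assumed unknown-day rates of 2% to 20% and on independence from event status. If days tend to be unknown because the event was continuing, the overstatement is smaller.

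A reader might infer that the primary safety result is compromised. It is not. The primary endpoints are numbers and percentages of participants with events, and those and their exact confidence intervals do not use 6.2.2. No hypothesis is tested and the sample size is untouched. This is a reporting defect in descriptive duration tables, worth correcting because it needs no new data.

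**What to change.** Amend SAP 6.2.2 so that each solicited AE has two labelled duration rows:

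1. **Recorded-day duration:** days marked 'Yes', plus unknown days lying between two 'Yes' days. The 4-day and 5-day examples are unchanged. Participants with leading question 'Yes' but no 'Yes' day are left out of n for this row and reported as duration unknown, so the third example no longer contributes 7 days here.
2. **Worst-case duration:** the current rule, named as such.

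Beside them, state how many durations include at least one unknown day.

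The cost is one extra derivation and row on data already collected, and a few participants without a recorded-day duration. The recorded-day row may understate duration when recording stopped during an ongoing event, which is why both rows should be shown.

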6.2.3. Handling of Missing Data

It is optimal to prevent missing data, to the extent possible, through strategies set forth in the design and conduct of a trial. For the current trial, we will aim to minimize missing information; for a given participants and a given immunogenicity measurement, missing or non-evaluable measurements will not be replaced.

The data will be analyzed as they are recorded in the trial eCRF. The number of missing values for data elements will be reported in tables and listings. Missing relationship with study vaccine, and outcome of unsolicited AEs will not be replaced and will appear as 'Missing' when displayed in a listing.

6.2.3.1. Handling of Missing Severity of AE

Estimate the missing severity of all kinds of AEs (solicited and unsolicited) by the maximal severity/grade observed in the overall population.

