5.5.2 Method of Detecting AEs and SAEs

A diary card will be used in this trial to capture solicited and other AEs. In addition to the participant completing and returning the diary card, the Investigator will record any occurrence of SAEs into the participant's eCRF to minimize potential missing data (e.g., when a participant's hospitalization prevents the completion of the diary). An AE that is assessed as severe should not be confused with a SAE. Severity is a categorization used for rating the intensity of an event; and both AEs and SAEs can be assessed as severe. An event is defined as 'serious' when it meets 1 of the pre-defined outcomes as described above ([Section 5.5](#)).

Assessment of Intensity

The intensity of the following solicited AEs will be assessed as described:

Table 3. Intensity Scales for Solicited Events in Adults 18 years of Age or More

Event	Intensity Grade	Parameter
Pain at administration-site	0	None
	1	Mild: Any pain neither interfering with nor preventing normal everyday activities
	2	Moderate: Painful when limb is moved and interferes with everyday activities
	3	Severe: Significant pain at rest. Prevents normal everyday activities
Headache	0	Normal
	1	Mild: Headache that is easily tolerated

CONFIDENTIAL
Phase IV Clinical Trial Protocol

GlaxoSmithKline
 A phase IV trial of *Fluarix Tetra* in Indian
 adults aged 65 years and older
 Version 2.0, dated: 05 May 2023
 Protocol/ Study No.: 218702
 Page 42 of 74

Event	Intensity Grade	Parameter
	2	Moderate: Headache that interferes with normal activity
	3	Severe: Headache that prevents normal activity
Fatigue	0	Normal
	1	Mild: Fatigue that is easily tolerated
	2	Moderate: Fatigue that interferes with normal activity
	3	Severe: Fatigue that prevents normal activity
Muscle ache all over body	0	Normal
	1	Mild: Muscle aches that are easily tolerated
	2	Moderate: Muscle aches that interfere with normal activity
	3	Severe: Muscle aches that prevent normal activity
Joint pain	0	Normal
	1	Mild: Joint pain that is easily tolerated
	2	Moderate: Joint pain that interferes with normal activity
	3	Severe: Joint pain that prevents normal activity
Shivering (chills)	0	Normal
	1	Mild: Shivering (chills) that is easily tolerated
	2	Moderate: Shivering (chills) that interferes with normal activity
	3	Severe: Shivering (chills) that prevents normal activity
Sweating	0	Normal
	1	Mild: Sweating that is easily tolerated
	2	Moderate: Sweating that interferes with normal activity

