4.2.2. Main Analytical Approach

The primary endpoint analyses related to solicited AEs will be performed on the SSS. The primary endpoint analyses related to unsolicited AEs will be performed on the ES.

The number and percentage of participants reporting solicited administration-site AE (any, Grade 3, medically attended), systemic AE (any, Grade 3 or Grade 4, medically attended) and either administration-site or systemic AE (any, Grade 3, medically attended) during the follow-up period (Day 1 – Day 7) will be tabulated with exact Clopper-Pearson 95% CI.

The number and percentage of participants reporting at least 1 unsolicited AE (any, Grade 3, related, Grade 3 related, medically attended) classified by the Medical Dictionary for Regulatory Activities (MedDRA) during the 21-day follow-up period (Day 1 - Day 21) will be tabulated with exact 95% CI, overall and by MedDRA System Organ Class (SOC) and Preferred Term (PT).

The number and percentage of participants reporting at least 1 SAE (any, fatal, related, fatal related) during the trial period (Day 1 - Day 21) will be tabulated with exact 95% CI, overall and by MedDRA SOC and PT.

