4.4.1.4. Assessment of Intensity

Intensity for solicited AEs will be assessed as follows:

Table 1 Intensity scales for solicited events

Adverse Event	Intensity Grade	Parameter
Pain at administration-site	0	None
	1	Mild: Any pain neither interfering with nor preventing normal everyday activities
	2	Moderate: Painful when limb is moved and interferes with everyday activities
	3	Severe: Significant pain at rest. Prevents normal everyday activities
Headache	0	None
	1	Mild: Headache that is easily tolerated
	2	Moderate: Headache that interferes with normal activity
	3	Severe: Headache that prevents normal activity
Fatigue	0	None
	1	Mild: Fatigue that is easily tolerated
	2	Moderate: Fatigue that interferes with normal activity
	3	Severe: Fatigue that prevents normal activity
Myalgia	0	None
	1	Mild: Muscle aches that are easily tolerated
	2	Moderate: Muscle aches that interfere with normal activity
	3	Severe: Muscle aches that prevent normal activity
Arthralgia	0	None
	1	Mild: Joint pain that is easily tolerated
	2	Moderate: Joint pain that interferes with normal activity
	3	Severe: Joint pain that prevents normal activity
Shivering (chills)	0	None
	1	Mild: Shivering (chills) that is easily tolerated
	2	Moderate: Shivering (chills) that interferes with normal activity
	3	Severe: Shivering (chills) that prevents normal activity
Sweating	0	None
	1	Mild: Sweating that is easily tolerated
	2	Moderate: Sweating that interferes with normal activity

Adverse Event	Intensity Grade	Parameter
	3	Severe: Sweating that prevents normal activity
Gastrointestinal symptoms: nausea, vomiting, diarrhoea and/or abdominal pain	0	None
	1	Mild: Gastrointestinal symptoms that are easily tolerated
	2	Moderate: Gastrointestinal symptoms that interfere with normal activity
	3	Severe: Gastrointestinal symptoms that prevent normal activity
Redness at administration-site	Record greatest surface diameter in mm	
Swelling at administration-site	Record greatest surface diameter in mm	
Temperature*	Record temperature in °C/°F	

* Fever is defined as temperature $\geq 38.0^{\circ}\text{C}$ (100.4°F) by any route. The preferred location for measuring temperature will be the oral route.

The maximum intensity of administration-site injection site redness/swelling will be scored as follows:

- 0: ≤ 20 mm
- 1: > 20 to 50 mm
- 2: > 50 to 100 mm
- 3: > 100 mm

The maximum intensity of fever will be scored as follows:

- 0: $< 38.0^{\circ}\text{C}$ ($< 100.4^{\circ}\text{F}$)

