- 1: $\geq 38.0 - 38.4^{\circ}\text{C}$ ($\geq 100.4 - 101.2^{\circ}\text{F}$)
- 2: $\geq 38.5 - 38.9^{\circ}\text{C}$ ($\geq 101.3 - 102.1^{\circ}\text{F}$)
- 3: $\geq 39.0 - 40.0^{\circ}\text{C}$ ($\geq 102.2 - 104.0^{\circ}\text{F}$)
- 4: $> 40.0^{\circ}\text{C}$ ($> 104.0^{\circ}\text{F}$)

The maximum intensity of solicited systemic events will be collected as follows:

- 1: Mild
- 2: Moderate
- 3: Severe

Intensity for unsolicited AEs will be assessed as follows:

The investigator will assess the maximum intensity that occurred over the duration of the event for all unsolicited AEs (including SAEs) recorded during the study. The assessment will be based on the investigator's clinical judgement.

The intensity should be assigned to one of the following categories:

1 Mild = An AE which is easily tolerated by the participant, causing minimal discomfort, and not interfering with everyday activities.

2 Moderate = An AE which is sufficiently discomforting to interfere with normal everyday activities.

3 Severe = An AE which prevents normal, everyday activities. In adults, such an AE would, for example, prevent attendance at work/school and would necessitate the administration of corrective therapy.

Severity is classed as Grade 1(mild)/ Grade 2 (moderate)/ Grade 3 (severe) (increasing severity). If a patient has an unsolicited AE more than once within that SOC/PT, the unsolicited AE with higher grade will be used in the corresponding severity summaries. Highest severity from Day 1 to Day 7 (for solicited AEs), Highest severity beyond Day 7 (for solicited AEs) and Highest severity (for unsolicited AEs) will be presented in listing. AEs with Grade 3 will be summarized.

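### SAP 4.2.2 omits Grade 4 from the combined solicited row, and SAP 6.2.3.1 imputes missing grades from an undefined pool with no recorded-grade result beside it

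*SAP*

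**What the plan says.** **Grade rows.** For solicited AEs, SAP 4.2.2 tabulates an administration-site row with Grade 3, then "systemic AE (any, Grade 3 or Grade 4, medically attended) and either administration-site or systemic AE (any, Grade 3, medically attended". Unsolicited AEs have Grade 3 and Grade 3 related rows. All carry exact Clopper-Pearson intervals and belong to the primary analysis, although the endpoints defined in SAP 4.2.1 mention no grade.

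**Scales.** SAP 4.4.1.4 scores fever from 0 to 4 ("The maximum intensity of fever will be scored as follows"). Every other solicited event stops at 3. For unsolicited AEs, "Severity is classed as Grade 1(mild)/ Grade 2 (moderate)/ Grade 3 (severe) (increasing severity". The same section ends by saying that Grade 3 AEs will be summarised, without mentioning Grade 4.

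**Missing grades.** SAP 6.2.3.1 is one sentence: "Estimate the missing severity of all kinds of AEs (solicited and unsolicited) by the maximal severity/grade observed in the overall population". SAP 3 defines the Enrolled, Exposed, Per Protocol and Solicited Safety Sets; none is called the overall population.

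**Other missing AE attributes.** SAP 6.2.3 says "Missing relationship with study vaccine, and outcome of unsolicited AEs will not be replaced", and also "The number of missing values for data elements will be reported in tables and listings". SAP 4.4.1.4 adds that "Highest severity (for unsolicited AEs) will be presented in listing", without saying whether that grade is recorded or imputed.

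**The concern.** There are two separate faults.

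**(a) Combined row.** A union cannot be smaller than one of its parts. As written, the systemic row can exceed the combined row, because Grade 4 counts in one and not in the other. This needs no missing data.

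**(b) Imputation rule.** The rule does not name the analysis set. Nor does it say whether the maximum is taken over all AEs or separately for solicited and unsolicited AEs. Two programmers could produce different Grade 3 tables from the same data. On the literal all-AE reading, a fever grade can be passed to events that have no such grade. Imputed grades would also enter the primary Grade 3 rows, and their exact intervals would treat them as observed. No table on recorded grades stands beside them, although missing relationship and outcome are left as missing.

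At stake are the severe-event rows of a descriptive safety trial, where the percentages and intervals are themselves the result.

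**Working it through.** **Inputs.** N=250 enrolled and 200 evaluable (SAP 5); using 200 as the size of the Solicited Safety Set is an assumption. Two-sided 95% Clopper-Pearson intervals (SAP 4.1.1). Grade scales from SAP 4.4.1.4. All counts of severe or ungraded participants below are assumptions, because the documents give none.

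**Formula.** For x of n, the lower limit is the 0.025 quantile of Beta(x, n−x+1) and the upper limit is the 0.975 quantile of Beta(x+1, n−x).

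**Check on the plan's own figure.** SAP Table 2, 1% row: x = 250 × 0.01 = 2.5 gives 0.17% to 3.17%, width 3.00. The chance of at least one participant is 1 − 0.99^250 = 91.9%. Both match the table.

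**Step 1: one participant.** 1/250 = 0.4 points; 1/200 = 0.5 points.

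**Step 2: combined row, no imputation.** Assume N=250, two participants with Grade 3 systemic events, one other whose only severe solicited event is a Grade 4 fever, and no Grade 3 administration-site event.

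| Row | Count | Rate (95% CI) |
|---|---|---|
| Systemic, Grade 3 or 4 | 3 | 1.2% (0.25–3.47) |
| Combined, as written | 2 | 0.8% (0.10–2.86) |
| Combined, Grade 4 included | 3 | 1.2% (0.25–3.47) |

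**Step 3: where an imputed grade lands.** Take a participant with an ungraded AE and no recorded severe event.

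| Pool maximum | Ungraded AE | Result under the current rule |
|---|---|---|
| 2 or lower | any | no change to the Grade 3 rows |
| 3 | any | added to the relevant Grade 3 row |
| 4 (all-AE pool with one Grade 4 fever) | systemic, e.g. headache | in the systemic row, outside the combined row |
| 4 | administration-site pain | outside both the administration-site and combined rows |
| 4 | unsolicited | outside the unsolicited Grade 3 rows |

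In the last three lines, a rule meant to be conservative removes the participant from one or more Grade 3 rows.

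**Step 4: illustrative size when the pool maximum is 3.** Assume one recorded Grade 3 participant plus m participants whose only Grade 3 is imputed.

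| m | N=250 | N=200 |
|---|---|---|
| 0 | 0.4% (0.01–2.21) | 0.5% (0.01–2.75) |
| 1 | 0.8% (0.10–2.86) | 1.0% (0.12–3.57) |
| 3 | 1.6% (0.44–4.05) | 2.0% (0.55–5.04) |

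**Step 5: both faults together.** Add to Step 2 three more participants, each with an ungraded systemic AE set to a pool maximum of 4. The systemic row becomes 6/250 = 2.4% (0.89–5.15), while the combined row stays at 2/250 = 0.8% (0.10–2.86).

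**The case against.** **Missing grades should be rare, and the route to imputation is narrow.** Under SAP 6.2.1 a solicited event whose leading question is unanswered or unknown counts as no occurrence, so a blank diary creates no ungraded event. Protocol 5.5.2 has the investigator grade every unsolicited AE, including SAEs. Edit checks (Protocol 7.6) and diary review at Day 22 should find gaps. The rule acts only on an AE recorded as present but ungraded. This stands, and it limits the weight of the point.

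**Worst-case assignment is defensible for safety data.** This also stands, and the rule should be kept. A reader might take the protocol's phrase "when a participant's hospitalization prevents the completion of the diary" as evidence that missing grades will be the severe ones. It does not show that: the phrase explains why the investigator also enters SAEs in the eCRF, precisely to limit missing data. That missing grades could be the severe ones is a possibility, not something the documents predict.

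**The extent of imputation would not be hidden.** Missing counts are required in SAP 4.1.1 and 6.2.3, so the recorded rate could be bounded. That is true, but a bound is not a tabulated rate with its interval, and nothing requires imputed grades to be marked.

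**The combined row may simply be shorthand.** Possibly, but the same sentence separates Grade 3 from Grade 3 or Grade 4, and SAP 4.4.1.7 writes Grade 3 or 4 for individual general events. An oversight is more likely, and it still needs correcting.

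**Conclusion.** Both passages are wrong as written, and both faults are minor. That the text is faulty is certain; that any result will change is not.

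The row mismatch changes a number only if a participant has a Grade 4, recorded or imputed, and no Grade 3 solicited event. The imputation matters only if an AE is recorded as present but ungraded; with none, its effect is zero. The only sizes that follow from the documents are 0.4 points per participant at N=250 and 0.5 at an assumed 200. The other rates above rest on assumed counts.

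A reader might infer that the primary safety results are inflated or unreliable. The documents do not support that: the endpoints carry no grade, any-grade, medically attended and SAE rates do not change, and no missing-grade rate is given.

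**What to change.** 1. **SAP 4.2.2:** label the combined row *Grade 3 or Grade 4*. Align the closing sentence of SAP 4.4.1.4, which names Grade 3 only.
2. **SAP 6.2.3.1:** keep the conservative rule but name the pool and cap it, for example: *A missing grade is set to the highest grade observed among all solicited AEs in the SSS (for solicited AEs) or all unsolicited AEs in the ES (for unsolicited AEs), capped at the top of that event's own scale.* A pool limited to the same event or preferred term would also be unambiguous, but it would no longer be worst case: it could assign Grade 1, or leave the grade missing where no other report exists.
3. **Tables:** show the Grade 3 rows also on recorded grades, with a *grade missing* row. Use all participants in the analysis set as the denominator in both versions, because the default in SAP 4.1.1 counts only those with non-missing data.
4. **Listings:** flag imputed grades.

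Cost: SAP wording, one extra table and a listing flag; data collection does not change. Recorded-grade rates may understate severity if the missing grades are the severe ones, which is why the imputed table stays beside them.
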